2.7. Interventions

After the blinded baseline assessment, participants are randomized into two arms:

Arm A: Immediate start group (see Fig. 1). Those randomized into the immediate start group will receive eCBT followed by TAU. The eCBT treatment manual (see Table 1 for a short summary of the session structure) is an adjusted version of previously published treatment manuals for neuropsychiatric symptoms in PD, to be tailored to the preferences and needs for each participant. This manual encompasses modules from manuals for both depression in PD and anxiety in PD [6,9]. Out of the nine modules in the manual, 5 are considered “core modules”, while 4 can be offered depending on the patients

[figure not shown]

Fig. 1. Flow chart of crossover trial.

Table 1
Summary of the cognitive behavioural therapy sessions.

Session	Core modules	Aim	Estimated duration
1	x	Introduction, psychoeducation and motivational enhancement.	75–90 min
2	x	Symptom monitoring and cognitive restructuring.	60 min
3–7		Behavioural activation, exposure, relaxation techniques and imaginal exposure, worry control.	60 min
8–9	x	Problem-solving, addressing executive functioning, self-management.	60 min
10	x	Review, relapse prevention planning.	60 min

* Module refers to the module in the treatment protocol.

individual needs, allowing for Individualization of the treatment course. The participant may include partners or caregivers in the treatment. The treatment is scheduled to be completed within 13 weeks, with a maximum of ten sessions during this period. Following each eCBT session, the participant will be asked to complete a short survey evaluating session acceptability and relevance, as well as the therapeutic alliance.

Arm B: Delayed start group. Those randomized to the waiting list control arm of the study will receive TAU and wait 14 weeks before receiving the intervention. TAU will include ongoing review by the patient's primary care physician, neurologist and PD nurse. TAU does not preclude clinically indicated adjustments to medication or specialist referrals, but physicians are asked to keep medication constant if possible. After the 14 week assessment, patients will start receiving eCBT, following the same procedures described for the immediate start group.

All therapists administering CBT are trained clinical psychologists at specialist or PhD-level. Before initiation of the treatment, each CBT-therapist will undergo individual training to ensure manual adherence, fidelity and quality. During the course of the trial, each therapist will receive regular supervision from an external CBT supervisor in order

to ensure continued adherence to the manual and fidelity to a CBT methodology. Supervision will be based on audio recorded therapy sessions (with consent from participants) and session records provided by the CBT-therapists, and rated using the Cognitive Therapy Adherence and Competence Scale.

Treatment adherence is monitored closely during the trial. At the beginning of each session the therapist will evaluate homework from the previous session with the patient. As a global measure of compliance, the therapist will assign a qualification of 'no', 'partial' or 'good adherence' to how the patient dealt with their homework assignment. In addition, all sessions considered core sessions need to be attended (five sessions). Missed appointments will be rescheduled where possible within the 14-week timeframe. The number of, and reason for missed optional sessions is also recorded. Participants who have not completed the five core sessions will be defined as non-completers. All costs associated with participation in this study is covered by the study.

2.8. Measures

Eligible, consenting participants will complete the baseline examination schedule over "Join.nhn.no", and receive instructions on how to use the videoconference call system. The baseline evaluation includes a clinical evaluation and cognitive assessment, performed by trained study nurses blinded for treatment allocation. For a detailed description of the examination schedule, please refer to Table 2.

2.9. Technical solutions and data storage

The ePark-CBT study will utilize two technical solutions, the video call platform "Join.nhn.no" by Norsk Helsenett (NHN), and the data-gathering platform TSD – Services for Sensitive Data by the University of Oslo (UiO). The video call platform "Join.nhn.no" by NHN offers end-to-end encrypted virtual meeting-spaces, well suited for online therapy and clinical follow up. This technology was implemented in most Norwegian health regions during the spring of 2020, and is now commonly used in clinical practice. The video call platform will be used to complete clinical evaluation at baseline (T1) and at follow up assessments (T2 to T4), as well as for the clinical intervention. The TSD - Services for

Table 2
Overview of the examination schedule.

Name of test	Test information			Time of assessment			
	Measure of	# of items	Rating type	Baseline	14 weeks	28 weeks	42 weeks
Background and clinical information							
Semi-structured interview for demographics	Demographics		Clinician	x	x ^a	x ^a	x ^a
MDS-Unified Parkinson's Disease Rating Scale (MDS-UPDRS) Part 1 – interview part [25]	Non-motor aspects of PD	6	Clinician	x			
Structured clinical interview for DSM-5 and diagnostic evaluation of depressive symptoms [11,26]	Diagnostic criteria for depression	12	Clinician	x			
Montreal Cognitive Assessment® Blind version (MoCA-B) [27]	Cognitive functioning	9	Clinician	x			
MDS-UPDRS Part 1 – selfreport [25]	Non-motor aspects of PD	20	Self	x			
Primary outcomes							
Clinical Global Impression Scale Severity (CGI-S) [28]	Symptoms severity of depression	1	Clinician	x	x	x	x
The Hospital Anxiety and Depression Scale (HADS) [29]	Symptoms of depression and anxiety	14	Self	x	x	x	x
The 8-item PD Questionnaire (PDQ-8) [30]	Health related quality of life	8	Self	x	x	x	x
Secondary outcomes							
Automatic Thoughts Questionnaire-30 (ATQ-30) [31, 32]	Depressive thoughts	30	Self	x	x	x	x
The Behavioural Activation for Depression Scale (BADS) [33]	Behavioural activation and avoidance	25	Self	x	x	x	x
Questionnaire for Impulsive-Compulsive Disorders in Parkinson's Disease Rating Scale (QUIP-RS) [34]	Impulse control disorders	4	Self	x	x	x	x
The Parkinson Anxiety Scale (PAS) [35]	Anxiety symptoms	12	Self	x	x	x	x
The 20 item Negative Effects Questionnaire (NEQ) [36]	Adverse and unwanted effects for psychological treatments	20	Self		(x)*	x	x
Patient Reported Experience Measure (PREM)	Participants experiences	6	Self	Weekly, following each treatment session			
Working Alliance Inventory, short form (WAI) [37]	Working alliance between patients and the CBT-therapist	12	Self	Weekly, following each treatment session, completed by patient and CBT therapist			

*Will only be administered to patients in the intervention group at the 14 week assessment.

^a Only questions on medication use is administered.

Sensitive Data platform will be used to gather the informed consent, for the initial screening and to gather information about the acceptability and therapeutic alliance following each session. The TSD platform provides a secure environment that meets legal requirements regarding privacy and protection of sensitive data and includes a platform for gathering of survey-based data online, termed “Sikkert-Nettskjema TSD 2”. The TSD services are managed by the University of Oslo (UiO) in accordance with a data-management agreement between Helse Stavanger HF and UiO. The site and platform comply with the General Data Protection Regulation and Norwegian privacy protection laws.

Also, due to the online design of this study several additional security precautions will be in place before initiation of the study. These include procedures of how to address acute medical situations, such as suicidal ideation or acute psychosis. For each participants a security card, with emergency contacts, contact information to nearby emergency services, ambulatory mental health services and general practitioner, will be prepared before the initiation of interventions. These data will be gathered during the second screening/baseline assessment. In case of increased suicidal ideation during the course of treatment, clinicians will follow local clinical guidelines for increased suicidal ideation. Clinicians are free to admit patients to acute outpatient or inpatient care in case of acute suicidal ideation. Participants with acute suicidal ideation will be excluded from the study.

3. Analysis plan

All analyses in this project will be performed using IBM SPSS Statistics version 26.0.0.1 or R 4.2.1, or more recent versions if available. An alpha-level of 0.05 will be used to indicate statistical significance. Descriptive statistics will be summarized using means, median, standard

deviations and ranges for numerical variables, and frequencies and percentages for categorical variables. Relevant univariate and multivariate analytic strategies will be used to test hypotheses h^i - h^{viii} .

For aim 1 (h^i - h^{iii}), linear mixed model analysis (LMM) with maximum likelihood estimation, based on an intent-to-treat protocol, will be used to gauge the between-group differences from baseline to the 14 week follow up. LMM will limit the impact of type 1 errors, and fully use the available data (in case of missing data). A random intercept for each participant and random slope will be included if they enhanced the model fit (evaluated using Akaike’s information criteria and Schwarz’s Bayesian criterion). In these analyses, a sum score from the primary and secondary outcomes will be used as dependent variables, and with significant covariates including treatment group, age, gender, duration of PD, and medication use. Medication use will be converted to levodopa equivalent dosages, using previously described procedures [18]. This analysis will be repeated using a per-protocol approach, where only completers (completed all core sessions) are included. Effect sizes will be calculated using Cohen’s d , with pooled pre- and post-SD adjustment for sample size.

For aim 2 and 3, linear regression analysis will be used to estimate group differences in depression scores at the end of the study (h^{iv}), and the association between working alliance and acceptability (h^{viii}). Independent variables include, gender, treatment group, age, duration of PD and medication use. Predictors for treatment effect will be investigated using (h^v , h^{vi} and h^{vii}) LMM, as described above.

4. Discussion

CBT is the first line treatment of choice for depression in the general population [19], and a number of studies have confirmed its effectiveness in patients with PD [9,20,21]. The limited availability of this treatment, especially in specialized treatment centres, such as movement disorder clinics, motivated earlier trials to conduct CBT remotely, e.g. via telephone [6,8,22,23]. However, this is the first trial using video-assisted online CBT in this population. The great advantage of video-assisted CBT over telephone-administered CBT is the fact that patient and therapist are able to see each other, including facial expressions and body language, which may be beneficial for the working alliance. However, no information on how working alliance is affected by online-therapy exists in patients with PD.

This is the first RCT to evaluate the effectiveness of online video-assisted CBT for depressive symptoms in people with PD and to study working alliance in this online setting. By following a fully online design for gathering informed consent, assessment and treatment delivery, we are able to include patients nation-wide. This will increase the clinical applicability of our findings, and allows for future implementation in sparsely populated settings where clinical services may be physically located far away from the patient.

Choice of research design: Blinded, randomized controlled trials (RCTs) are considered the gold standard for ascertaining the efficacy and safety of a clinical intervention. The prospective RCT-design is well-suited method to evaluate the immediate and long-term effect of psychological interventions, including CBT [24,25]. For this trial, a delayed start design, where all participants over time receive the clinical intervention, was chosen for a number of reasons. Due to the duration of the trial (42 weeks) and relative high target N ($N = 120$), a parallel arm design is difficult to implement. Based on feedback from user representatives in the “reference group”, recruitment of participants would be difficult if participants are not guaranteed treatment during the course of the trial. Also, given the relatively long duration of this RCT, keeping participants away from treatment for an extensive period of time is ethically problematic. Furthermore, a delayed start design will enable us to control for natural remission of depressive symptoms by monitoring the development of depressive symptoms in a TAU-group over the first 14 weeks. Finally, we will be able to address the treatment response not only immediately after intervention but also in a longer time

perspective, particularly in the early intervention group.

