1.1. Study aims and hypotheses

We will conduct a remote, randomized, delayed start trial, in order to.

- I. Assess the effectiveness of online, video-assisted cognitive behavioural therapy (eCBT) for depressive symptoms in patients with PD.
- II. Assess long-term outcomes, and predictors of long-term outcomes, of eCBT for depressive symptoms in PD.
- III. Explore the impact and clinical correlates of eCBT working alliances in patients with PD.

For the first aim, we hypothesize that.

- i. eCBT will reduce the self-reported severity of depressive symptoms in patients with PD, as compared to patients in a control group receiving treatment as usual (TAU).
- ii. eCBT will reduce the observed severity of depressive symptoms in patients with PD, as compared to patients in a control group receiving TAU.
- iii. eCBT will improve self-reported health related quality of life in patients with PD, as compared to patients in a control group receiving TAU.

For the second aim, we hypothesize.

* Corresponding author. The Norwegian Centre for Movement Disorders, Stavanger University Hospital, [name].
E-mail address: [contact] ([name]).

- iv. Participants in group A (early eCBT) and group B (late eCBT) will have comparable depression scores 14 weeks following the eCBT intervention.
- v. A poorer long-term treatment response to eCBT for depressive symptoms is predicted by more severe self-reported comorbid symptoms of anxiety and impulse control disorders at baseline.
- vi. A better long-term treatment response to eCBT for depressive symptoms is associated with greater change in self-reported comorbid symptoms of anxiety and impulse control disorders at the time of treatment completion.

For the third aim, we hypothesize.

- vii. The quality of the therapeutic working alliance, as measured by patient self-report, as well as adherence levels, will significantly predict change in self-reported depression scores.
- viii. Patients self-reported working alliance scores will significantly predict the acceptability of eCBT, as defined by patient reported experience measures.

2. Methods

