2.2. Study design

This study is an online, randomized, delayed start trial of the effectiveness of eCBT for PD patients with depressive symptoms. N = 120 PD patients with depressive symptoms will be recruited from outpatient clinics and via self-referral in Norway, and randomized into two arms: (A) immediate 10-weeks eCBT with concurrent TAU and (B) a delayed start (14 weeks) of eCBT with TAU alone. Patients will be assessed at baseline before allocation to a specific treatment arm, with follow-up evaluations after 14, 28 and 42 weeks. See Fig. 1 for the study flow.

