2.5. Sample size and feasibility

A priori power calculations was performed using G*Power 3.1.9.2 [15,16]. Power analysis is based on power calculation for *t*-test, and it serves as a lower bound estimate of power as it applies as long as each patient has at least two measurements. Multiple observations per subject will increase the power and eliminate the impact of possible missing

observations. The study is powered to identify a mean difference in HADS-D score of 1.98 points, with $\alpha = 0.05$, power set to 80%, and a predicted effect size of Cohen's $d = 0.80$. Based on these calculations, the required number of participants is 84 (42 per group). Including $N = 60$ participants per group will allow for up to 30% dropout from the study, while retaining sufficient statistical power. Based on the large effect sizes observed in other RCTs investigating CBT for depression in PD [6–8], we expect the effect size to be larger and the drop out to be lower ($\approx 10\%$). Participants whom decide to leave the study prematurely will not be replaced by new participants, and their data will be included in the main analysis according to an intention-to-treat principle.

There is an estimated 7000 patients with PD in Norway, of whom about 3500 are members of the patient organization the Norwegian PD Association. With a conservative frequency of 30%, depressive symptoms would affect approximately >2000 Norwegian PD patients in general, and >1000 of the members of the Norwegian PD Association. While access to computers and adequate internet bandwidth is largely ubiquitous in a Norwegian setting, familiarity with online platforms and video-conferencing could still limit recruitment for this study. However, a recent nationwide survey using similar data-gathering tools demonstrated that a large proportion of the PD community manages to use the technologies employed in this study [17]. Thus recruitment of $N = 120$ participants for this study is thus considered feasible.

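### The early-versus-late eCBT comparison (hypothesis iv) is a last-visit regression with no baseline depression covariate, at a visit that does not match the hypothesis

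*Protocol*

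**What the plan says.** Hypothesis iv, under the second aim in Section 1.1, predicts that groups A and B "will have comparable depression scores 14 weeks following the eCBT intervention". Section 3 (Analysis plan) gives its analysis: "linear regression analysis will be used to estimate group differences in depression scores at the end of the study". The covariates follow: "Independent variables include, gender, treatment group, age, duration of PD and medication use". No baseline depression score is among them.

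Section 2.2 describes a baseline assessment "with follow-up evaluations after 14, 28 and 42 weeks", so the end of the study is week 42. Table 2 schedules HADS and CGI-S at all four visits.

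For aim 1, Section 3 chooses a linear mixed model, partly for its ability to "fully use the available data (in case of missing data"). It keeps that model for hypotheses v, vi and vii ("LMM, as described above"). Hypothesis iv gets neither the mixed model nor any statement on missing scores.

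Section 2.5 says that 60 "participants per group will allow for up to 30% dropout from the study" and expects about 10%. Of people who leave early it says that "their data will be included in the main analysis according to an intention-to-treat principle".

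**The concern.** Three features of the hypothesis-iv analysis look weak.

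- **Baseline.** The baseline value of the outcome is usually its strongest predictor. It is collected on everyone before randomisation, yet it is not in the listed model.
- **Missing scores.** An ordinary regression on one visit uses only people seen at that visit. Week 42 is where losses have accumulated most, and the protocol's own missing-data argument for the mixed model is not carried over to it.
- **Timing.** The hypothesis is set relative to the end of treatment, which differs by arm. The analysis is set at a common calendar visit.

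Hypothesis iv predicts similarity and states no margin. A wider interval makes a non-significant difference more likely, and that could be taken as support. Imprecision therefore works in favour of the hypothesis.

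**Working it through.** **The plan's own figure.** The protocol gives no precision figure for hypothesis iv. The nearest is the sample size in Section 2.5: 42 per group for d = 0.80, alpha 0.05 and 80% power. A two-sided two-sample t-test with those inputs needs 26 per group; 42 per group corresponds to 95% power. That mismatch is a separate matter, and nothing below depends on it.

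**Inputs.** SD = 1.98 / 0.80 = 2.475 HADS-D points (Section 2.5). Numbers at week 42: 60 × 0.9 = 54 per arm at 10% dropout and 60 × 0.7 = 42 at 30%. The baseline-outcome correlation ρ is not in the protocol; 0.3 to 0.7 is assumed.

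**Step 1: cost of omitting baseline.** SE = SD × √(2/n) without baseline, and that value × √(1 − ρ²) with it. At n = 42: 2.475 × √(2/42) = 0.540, and 1.96 × 0.540 = 1.06. The sample multiplier for equal precision is 1/(1 − ρ²).

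| ρ | Sample multiplier | Half-width, 42 per arm | Half-width, 54 per arm |
|---|---|---|---|
| baseline omitted | – | 1.06 | 0.93 |
| 0.3 | 1/0.91 = 1.10 | 1.01 | 0.89 |
| 0.5 | 1/0.75 = 1.33 | 0.92 | 0.81 |
| 0.7 | 1/0.51 = 1.96 | 0.76 | 0.67 |

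If the SD were 3.2 (the value at which 42 per group gives 80% power for 1.98 points), the half-widths at 42 per arm would be 1.37 without baseline and 1.19 or 0.98 with it (ρ = 0.5 or 0.7). The multipliers do not change.

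**Step 2: what the other visits add.** This was simulated with 4,000 trials per setting, 60 per arm, equal correlation between visits, a true week-42 difference of 0 and 30% random dropout. The empirical SEs, in SD units, were:

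| ρ | Week-42 regression, no baseline | Plus baseline | Likelihood analysis with earlier scores |
|---|---|---|---|
| 0.5 | 0.219 | 0.193 | 0.191 |
| 0.7 | 0.216 | 0.156 | 0.152 |

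The last step gains 1 − 0.191/0.193 = 1.0% and 1 − 0.152/0.156 = 2.6%. Nearly all the lost precision is recovered by the baseline covariate alone.

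**Step 3: dropout bias.** In the same simulation, dropout was then made to depend on the week-14 score, with the same slope in both arms (arm A is already treated by then, arm B is not). Bias of the regression without baseline:

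- 10% dropout: 0.024 and 0.034 SD (ρ = 0.5 and 0.7), or 0.024 × 2.475 = 0.06 and 0.034 × 2.475 = 0.08 points.
- 30% dropout: 0.059 and 0.075 SD, or 0.15 and 0.19 points.

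Adding baseline reduces the bias to 0.01–0.03 SD. The likelihood analysis with earlier scores has at most 0.002 SD.

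If score-dependent dropout occurs in arm A only, at 10% and a logit slope of 0.5 to 1 per SD, the bias is 0.07 to 0.20 points in size, and at most 0.04 once baseline is added. At 27 to 30% missing, stronger arm-specific mechanisms gave 0.35 to 0.74 points.

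**Step 4: timing.** Sections 2.6 and 2.7 place arm A's sessions within 13 weeks of baseline. Arm B starts after the week-14 assessment and follows the same procedures. With the treatment windows ending at about weeks 14 and 28, 14 weeks later is week 28 in arm A and week 42 in arm B. At week 42, arm A is about 42 − 14 = 28 weeks past treatment and arm B about 42 − 28 = 14. Sections 1.1 and 3 therefore describe different contrasts. This step needs no assumed correlation or dropout rate.

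**The case against.** The covariate list is introduced as what the variables include, so it need not be exhaustive. An analysis plan that is not shown could add baseline or a missing-data method. That limits how firmly the omission can be stated, but the protocol does fix the model type, the visit and a covariate list for this hypothesis. Hypothesis iv is also a second-aim question.

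Several stronger readings are tempting, and the documents do not support them.

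- **Discarding the other visits is what loses the precision.** It is not: Step 2 shows a gain of only 1 to 3% beyond baseline.
- **Dropout will materially bias the result.** The protocol expects about 10% loss, where the simulated bias is small. Section 2.10 removes participants with acute suicidal ideation, so severity-related loss is conceivable. Nothing in the protocol supports a particular dropout slope or opposite directions by arm.
- **The plan breaks its intention-to-treat promise.** Section 2.5 makes that promise for the main analysis only.
- **The analysis is restricted to completers.** In this protocol completers are those who attended the five core sessions. Section 3 does not limit hypothesis iv to them; anyone with a week-42 score counts.
- **Omitting baseline biases the comparison.** In a randomised comparison it costs precision and does not in itself create bias.

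**Conclusion.** The point stands as an inefficient analysis choice and a contradiction to reconcile.

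Omitting baseline depression is the main statistical cost: a sample multiplier of about 1.3 to 2.0 at an assumed correlation of 0.5 to 0.7, falling to 1.10 at 0.3. Leaving out people without a week-42 score adds a risk of bias, below 0.1 point at 10% dropout with a common mechanism, up to about 0.2 if dropout is arm-specific, and about 0.15 to 0.19 at 30%. Larger values need steep arm-specific dropout. All bias figures rest on assumed correlations and mechanisms. They refer to the week-42 contrast; the contrast in Section 1.1 was not quantified.

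The timing mismatch follows from the text alone. The aim-1 comparison is not affected.

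**What to change.** Estimate hypothesis iv from one linear mixed model on all randomised participants, with arm, visit and arm-by-visit, using HADS-D. Enter baseline HADS-D once only, in one of two ways:

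- as a covariate, with weeks 14, 28 and 42 as responses; or
- as the first of four responses, with the baseline means constrained equal across arms.

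Do not use it as both response and covariate. If all four visits are responses and the arms are left free at baseline, the week-42 difference in means gets no baseline adjustment: its SE would be about 2.475 × √(2/60) = 0.452 even with complete data.

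Reconcile Sections 1.1 and 3 on the time point. Report the contrast that matches Section 1.1 (arm A at week 28 against arm B at week 42) and the week-42 contrast, each with a 95% CI. The first aligns time since treatment but not time since randomisation, and the second does the reverse, so the two should be read together.

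State that a non-significant difference is not evidence of comparability. If a positive claim of comparability is intended, a margin has to be set in advance and the interval judged against it.

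The cost is analysis wording only. The visits, the scale and the model type are already in the plan.
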